**PE37: A multicenter randomized trial of screening with sFlt1/PIGF and selective labor induction to prevent preeclampsia at term.**

Primary Site:
 
BCNatal (Hospital Clínic and Hospital Sant Joan de Déu) and Hospital Sant Pau, Barcelona, Spain

Principal Investigators:
 
[name], [name] and [name]

Disease Studied and Intervention
 
Preeclampsia in late pregnancy

Cohort:
 
Non-selected nulliparous pregnant women routinely attended at 35-36 weeks' gestation and randomized to revealed versus concealed maternal angiogenic factors levels.

Inclusion and Exclusion Criteria:
 
Inclusion criteria:
 
 
1. Nulliparous women
 
2. Singleton pregnancies
 
3. >18 years old
 
4. 35.0-36.6 weeks of gestation
 
5. Maternal written consent form
 
6. Planned vaginal delivery
 
 
Exclusion criteria:
 
-Any maternal or fetal complications that require labor induction before 38 weeks according to local institutional protocols (including established preeclampsia).

Study Type
 
Prospective, open-label randomized multicentre study with parallel groups conducted at BCNatal (Hospital Clínic and Hospital Sant Joan de Deu) (Barcelona), Hospital Sant Pau (Barcelona), Hospital la Paz (Madrid), Hospital del Mar (Barcelona), Hospital la Fe (Valencia), Hospital Son Llatzer (Mallorca), Hospital Can Ruti (Badalona), Hospital Clínico de Zaragoza, Hospital Arrixaca de Murcia and Complejo Hospitalario Universitario Insular Materno Infantil (Las Palmas de Gran Canaria) (Spain), Institute for the Care of Mother and Child, Prague, Prague, Czechia, Centre of Postgraduate Medical Education, Obstetrics and Gynecology and Perinatal Medicine, Warsaw, Poland;

Gynecology and Obstetrics - CHU Liège; Belgium.

Intervention
 
 
Revealed arm: Blood sampling at 35+0-36+6w to determine sFlt-1/PlGF ratio. The result will be known by managing clinicians and, if >90th centile, labour induction from 37+0 weeks will be offered.
 
Concealed arm: The result of sFlt1/PlGF ratio will be unknown. Routine follow-up
 

Duration
 
3 years

Date Of First Enrolment
 
February 2021


Estimated Sample Size
 
8302 nulliparous women are needed to demonstrate a 50% reduction of development of PE (from 1.5%) with a 90% power and a 5% alpha-risk. Assuming a 10% loss, we estimated a sample size of 9132 women.

Study Aims
 
To evaluate the impact of a policy of induction of labour from 37 weeks of gestation in nulliparous women at risk for preeclampsia as defined by a sFlt1/PlGF ratio >90th centile at 35-36 weeks of gestation on the prevalence of term PE.
 
As secondary objectives, the study will evaluate the impact of the sFlt1/PlGF screening on:
 
 
Cesarean section rates
 
Perinatal morbidity
 
Maternal pregnancy-related morbidity.
 
Maternal post-pregnancy endothelial function.
 
Cost-efficiency analysis (hospital maternal and neonatal stay and incurred costs).
 
Maternal experience.
 

### Executive summary

- Preeclampsia (PE) affects ~5% of pregnancies. Although improved obstetrical care has significantly diminished associated maternal mortality, PE remains a leading cause of maternal morbidity and mortality in the world.
- Term PE accounts for 70% of all PE and a large proportion of maternal-fetal morbidity related with this condition. Prediction and prevention of term PE remains unsolved.

- Previously proposed approaches are based on combined screening and/or prophylactic drugs, but these policies are unlikely to be implementable in many world settings.
- Recent evidence shows that sFlt1-PlGF ratio at 35-37w predicts term PE with 80% detection rate.
- Likewise, recent studies demonstrate that induction of labor (IOL) from 37w is safe.
- The investigators hypothesize that a single-step universal screening for term PE based on sFlt1/PlGF ratio at 35-37w followed by IOL from 37w would reduce the prevalence of term PE without increasing cesarean section rates or adverse neonatal outcomes.
- The investigators propose a randomized clinical trial to evaluate the impact of a screening of term PE with sFlt-1/PlGF ratio in asymptomatic nulliparous women at 35-37w. Women will be assigned to revealed (sFlt-1/PlGF known to clinicians) versus concealed (unknown) arms. A cutoff of >90th centile will be used to define high risk of PE and offer IOL from 37w.
- If successful, the results of this trial will provide evidence to support a simple universal screening strategy reducing the prevalence of term PE, which could be applicable in most healthcare settings and have enormous implications on perinatal outcomes and public health policies worldwide.

## **Background**

### **Preeclampsia at term as an unsolved problem with a high health impact**

Preeclampsia (PE), defined as the presence of hypertension with other signs of endothelial systemic damage, affecting 5-10% pregnancies and remains one of the most prevalent serious complications of pregnancy. Despite improved obstetrical care, PE remains a leading cause of maternal morbidity and mortality worldwide. While early-onset PE is the most feared form of the disease, a remarkable 70% of total cases occur at term (1), accounting for a large proportion of adverse maternal outcomes (2). Identification of term PE relies on clinical follow up and detection of hypertension in a pregnant woman, followed by elective delivery. This policies have been shown to reduce the rates of severe maternal complications and is now standard practice (3), but still result in a significant proportion of

cases detected too late (4). One important reason is that most instances of term PE occur in women without risk factors. Aside from the rates of severe complications, the diagnosis of PE entails a traumatic experience for women affecting their pregnancy and birth experience and their pathway to motherhood (5) (6). Moreover, PE has a significant impact in healthcare costs (7) and suffering PE predisposes women for long-term cardiovascular adverse outcomes later in life.

#### **Angiogenic factors: PlGF and sFlt1 and their role as specific biomarkers of PE**

For more than 100 years, PE was diagnosed by hypertension and proteinuria in a pregnant woman. Angiogenic factors have recently emerged as the most specific biomarkers of PE ever described, so much that are being incorporated as an essential component in the prediction, diagnosis and even prognosis of PE by all relevant international societies.

Under normal conditions, angiogenic factors released by the placenta maintain a balance in maternal blood whereby the effects of the proangiogenic Placental Growth Factor (PlGF) prevail over those of the antiangiogenic soluble fms-like tyrosine kinase 1 (sFlt1). In preeclampsia, placental inflammation and increased oxidative stress result in the release of larger amounts of sFlt1 over PlGF. Thus, the ratio sFlt1/PlGF reflects placental and endothelial functioning, the end-organs of preeclampsia, and it is a consubstantial feature of the disease.

This ratio has now been accepted as a criterion for the diagnosis of PE in suspected cases (12). According to recent studies in large populations, the capacity of an abnormal ratio in ruling-in the disease is intermediate-large (as reflected by a +LHR of 8.2), while its capacity in ruling it out is large (–LHR 0.2). This is in line with the high performance shown by the sFlt1/PlGF ratio to predict term PE at 35-36w. Thus, the sFlt1/PlGF ratio might represent a

feasible universal approach for the detection of risk by identifying term PE in its pre-clinical stages.

### **Justification of the study**

Finding an effective prediction and prevention for term PE remains an unsolved challenge. From previous recent evidence it seems clear that prediction very close to term may achieve a high detection rate, but there is no evidence as to which strategy might be effective in preventing PE in high-risk women. The investigators postulate that a solution that would be applicable in most settings worldwide would require a simplified, pragmatic, approach. The rationale of this proposal is that PE could be reduced with a single-step lab test screening followed by induction of labor (IOL).

**A single-step lab measure to detect PE.** Combined algorithms using angiogenic factors with Doppler ultrasound and maternal features seem to achieve the highest performance in detecting pre-clinical PE. However, the need to train staff and change pregnancy care protocols renders difficult generalization in high-resource and even more low-resource settings. On the contrary, single lab tests can be more easily incorporated into the mainstream clinical practice and provide a widespread solution for high-resource settings and specially sub-optimal healthcare systems heavily affected by the consequences of term PE. Angiogenic factors are the obvious candidate for these purposes. The sFlt1/PIGF ratio at 35-36w predicts term PE with a DR of 82% and is a standardized lab test nowadays, realizable by ELISA with widely available automated lab platforms. Normal values in late pregnancy have been reported and are fairly similar among different populations. As preliminary research for this study, the investigators have confirmed that the gestational-age adjusted normal values of sFlt1/PIGF matched quite remarkably those previously published in different populations across Europe. A one-step screening with sFlt1/PIGF would select a 5-10% of the population with the highest risk for PE.

### **IOL at 37 weeks as an intervention in women at high-risk for PE.**

Previous trials based on statins have failed to show a reduction of PE in high-risk women. IOL at 37 weeks is an alternative to avoid PE in those high-risk women. IOL has consistently been demonstrated to be safe (13) and does not affect long-term maternal quality of life (14). Both the HYPITAT and the DIGITAT randomized trials showed that IOL did not increase

caesarean rates or adverse neonatal outcomes (15). A recent large randomized trial in the US has shown that even in low-risk women, universal IOL decreased cesarean section rates and was well accepted (16). While in low-risk pregnancies labour induction has been found to be beneficial from 39 weeks (ARRIVE study), in women with placental-related conditions such as hypertension (HYPITAT) or small-for-gestational age (DIGITAT) it is 37+ weeks when the trade-off between neonatal and maternal benefits makes induction recommendable.

Therefore, the investigators hypothesize that a single-step universal screening for term PE based on sFlt1/PIGF ratio at 35-36.6 w followed by IOL at 37w in those women found to be at high risk might represent a feasible and reproducible strategy, applicable worldwide, to reduce the prevalence of term PE without increasing cesarean section rates or adverse neonatal outcomes.

### Objectives

To evaluate the impact of a policy of induction of labour from 37 weeks of gestation in nulliparous women at risk for preeclampsia as defined by a sFlt1/PIGF ratio >90th centile at 35-36 weeks of gestation on the prevalence of term PE.

As secondary objectives, the study will evaluate the impact of the sFlt1/PIGF screening on:

1. Cesarean section rates
2. Perinatal morbidity
3. Maternal pregnancy-related morbidity.
4. Maternal post-pregnancy endothelial function.
5. Cost-efficiency analysis (hospital maternal and neonatal stay and incurred costs).
6. Maternal experience.

### METHODOLOGY

#### Study design

Prospective, open-label randomized study with parallel groups.

#### Study population:

Non-selected nuliparous pregnant women routinely attended at 35-36 weeks' gestation and randomized to revealed versus concealed maternal angiogenic factors levels.

#### Inclusion and Exclusion Criteria:

Inclusion criteria:

- Nulliparous women

PE37 Trial 19 Feb 2021 Version 7.0

- Singleton pregnancies
- >18 years old
- 35.0-36.6 weeks of gestation
- Maternal written consent form
- Planned vaginal delivery

Exclusion criteria:

- Any maternal or fetal complications that require labor induction before 38 weeks according to local institutional protocols (including established preeclampsia).

### 90th centile of sFlt1/PIGF ratio.

Calculation of sFlt1/PIGF ratio centile has been obtained from 600 serum samples from women with uneventful pregnancy outcomes attending BCNatal between 35.0 and 38.0 weeks of gestation (Figure 1). Samples were stored in BCNatal biobank and measured using automated electrochemiluminescence immunoassays on the Roche cobas platform (Roche Diagnostics GmbH, Mannheim, Germany) at the Biochemistry Dept. of Sant Pau Hospital. Intra- and interassay coefficients of variation were found to be <5%. Quantile regression analysis was applied for the establishment of the 90th centile value of sFlt1-1/PIGF at the midpoint of each gestational week. This value was considered as the cut-off for all the week interval: 25 between 35+0 and 35+6; and 35 between 36+0 and 36+6.

[figure not shown]

Figure 1. sFlt1/PIGF ratio from 35 to 38 weeks of gestation in normal pregnancies.

**Predictive variables**

Main predictive variable: study group, i.e. type of intervention.

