**Sample size calculation**

8302 nulliparous women are planned to be include demonstrating a 50% reduction of development of PE (from 1.5%). Assuming a 10% loss, the investigators estimated a sample size of 9132 women.

*R Syntax:*

```
library(SampleSize4ClinicalTrials)

ssc_propcomp (1L,ratio=1,alpha=0.05,power=0.9,p1=0.0075, p2=0.015)
```

Under a non-inferiority hypothesis testing design, assuming a composite adverse neonatal outcome incidence of 1% in the revealed group, 0.5% in the concealed risk and a prespecified non-inferiority margin of 0.25%; this sample size (4151 per arm) would result in a power of 99% to reject the null hypothesis that the reveal strategy increases the neonatal complications.

*R Syntax:*

```
library(SampleSize4ClinicalTrials)

ssc_propcomp (3L,ratio=1,alpha=0.05,power=0.99,p1=0.005, p2=0.01, delta=0.0025)
```

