### **Statistical analysis**

Once all evaluations have been performed and laboratory determinations have been completed, the evaluation and analysis of the results will be carried out, with assistance of the Bioinformatics Department of the Institut de Recerca, and the Research Support Unit. Statistical analyses will be performed with the statistical package IBM® SPSS® Statistics Version 25 (IBM Corporation) or Open-source software (The R Foundation for Statistical Computing) will be used for all computations and graph construction (R V2.15.1). Statistical analysis will be based on the originally assigned groups (intention-to-treat). Normality of the distribution of variables will be evaluated with the Kolmogorov-Smirnov test. A binomial distribution model will be used to determine the 95% CI of proportions. Student's t-test (or non-parametric Mann-Whitney U test) and Pearson's  $\chi^2$  test or linear-by-linear  $\chi^2$  test (for trends across ordered categories) will be performed for univariate between-group comparisons of quantitative or qualitative variables, respectively. A mixed-effects logistic regression analysis of the incidence of live-birth with fixed effects for allocation group will be

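### A cheap gain, not an error: pre-specify a key secondary comparison of term preeclampsia among screen-positive women of both arms, and adjust the all-women primary comparison for screen status

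*Protocol*

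**What the plan says.** The section Predictive variables fixes the contrast: "Main predictive variable: study group, i.e. type of intervention". The main outcome is development of term preeclampsia. Under Statistical analysis, the tests named "will be performed for univariate between-group comparisons of quantitative or qualitative variables", and groups are analysed as assigned.

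The sample size rests on the same all-women contrast: "ssc_propcomp (1L,ratio=1,alpha=0.05,power=0.9,p1=0.0075, p2=0.015" under Sample size calculation, "with a 90% power and a 5% alpha-risk" in the synopsis, and "this sample size (4151 per arm".

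The synopsis (Intervention) and the Executive summary restrict the offer of induction to revealed-arm women above the 90th centile. Justification of the study puts the share selected at 5-10%. The Objectives describe a policy of induction "in nulliparous women at risk for preeclampsia as defined by a" high ratio, and its effect on the prevalence of term preeclampsia. Women are "randomized to revealed versus concealed maternal angiogenic factors levels" (Study population), which implies that a ratio exists in both arms. The synopsis, however, writes out blood sampling for the revealed arm only.

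The listed secondary outcomes do not include term preeclampsia among screen-positive women.

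**The concern.** Most women in the comparison are offered the same care in both arms. If screen-negative women have the same preeclampsia risk in both arms, their cases add variance to the contrast and no effect. At 62% detection they supply 38% of concealed-arm cases.

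At that detection rate, the planned halving of the overall rate requires about 81% of preeclampsia in flagged women to be averted. Induction is offered rather than assured, so a smaller effect is plausible. The all-women test then loses power quickly, and a trial of about 9,000 women could end inconclusive while its screen-positive women carry a clear answer.

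The ratio is measured at 35-36 weeks, before any induction. If it is obtained in the same way in both arms, screen-positive women are a baseline stratum and are comparable by randomisation. Naming that comparison in advance keeps it from being dismissed later as post hoc.

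**Working it through.** **Inputs from the protocol.** Rates 1.5% and 0.75%, alpha 0.05, power 90%, 1:1, 4151 per arm (Sample size calculation). Screen-positive share 10%, or 5-10% (Executive summary; Justification of the study). Detection rate of the ratio alone: 62% within 4 weeks and 82% within 2 weeks (Table 1), and 80% (Executive summary).

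**Assumptions.** No effect in screen-negative women. The smaller effects (60% or 50% of flagged cases averted) are illustrative; the protocol does not state them.

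**1. The protocol's own figure.** Two-sided, unpooled variance: n = (1.960 + 1.282)² × (0.015×0.985 + 0.0075×0.9925) / 0.0075² = 4150.4, so 4151 per arm and 8302 in total. Power at 4151 per arm is 90.0%. The stated figure reproduces.

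**2. Which detection rate fits the 1.5% rate.** Table 1 implies a base rate of PPV × positive rate / detection. The 4-week row gives 8.8% × 10% / 62% = 1.4%; the 2-week row gives 3.8% × 10% / 82% = 0.46%. The 62% row matches the planning rate better. The 80-82% figures are carried as the alternative.

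**3. Screen-positive women, 62% detection.** Number per arm: 10% × 4151 = 415. Concealed-arm risk: 1.5% × 0.62 / 0.10 = 9.3%. Power = Φ(difference/SE − 1.960), with SE = √[(p₁(1−p₁) + p₂(1−p₂))/n].

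- Planned effect: an overall difference of 0.75 points placed wholly in the 10% stratum is 7.5 points, so 9.3% v 1.8% (81% reduction). SE = 0.0157, z = 4.78, power 99.8%. All women: 90.0%.
- 60% averted: 9.3% v 3.7%. SE = 0.0170, z = 3.28, power 90.7%. Overall 1.5% v 0.94% (37% reduction); all women 63.9%.
- 50% averted: 9.3% v 4.65%, power 75.2%. All women: 47.4%.

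**4. Varying the detection rate (10% positive).**

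| Detection | Planned effect: screen-positive v all women | Same smaller overall effect (1.5% v 0.94%): screen-positive v all women |
|---|---|---|
| 62% | 99.8% v 90.0% | 90.7% v 63.9% |
| 80% | 97.7% v 90.0% | 79.8% v 63.9% |
| 82% | 97.4% v 90.0% | 78.6% v 63.9% |

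If the share of flagged cases averted is held at 60% instead, 80% detection gives 96% v 87%.

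**5. Varying the positive rate.** At 5% positive (208 per arm) and 62% detection: 99.9% for the planned effect and 92.9% for the smaller one.

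**6. Adjusting the all-women comparison for screen status.** The variance of the post-stratified risk difference sums the stratum variances weighted by stratum share. At 10% positive and 62% detection, power rises from 90.0% to 90.9% and from 63.9% to 65.3%. At 82% detection it reaches 91.9% and 67.0%. The gain is about 1-3 points.

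**The case against.** The strongest reply is that nothing here is wrong. The objective is the effect of a policy on the prevalence of term preeclampsia in a non-selected population, and an all-women intention-to-treat comparison answers exactly that. A stratum analysis is commonly left to the statistical analysis plan, which is not shown, and the available Statistical analysis text breaks off mid-sentence. Its absence cannot be asserted. All of this stands, and it is why the point is an improvement and not a fault.

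A reader might infer that the stratum comparison lifts the trial's power from 90% to over 99%. It does not. The two tests address different hypotheses, and the power of the primary is unchanged apart from the small gain from adjustment. A key secondary result also cannot rescue a failed primary.

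A reader might also infer that only 10% of women can receive different care. The documents support less. Only about 10% are offered induction, but the trial is open label and clinicians see every revealed-arm result, so care of screen-negative women could change too. The calculation assumes no effect in them.

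Finally, feasibility is implied but not stated. Sampling is described only for the revealed arm, and the order of sampling and allocation is not given. If concealed-arm samples were not assayed, or ratios were missing to different degrees by arm, the stratum would lose its randomised comparability or cost far more than wording. This stands as a condition of the proposal.

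**Conclusion.** The all-women comparison is valid and should remain primary. A pre-specified comparison in screen-positive women of both arms is a worthwhile, inexpensive addition. It had more power than the all-women test in every scenario with a 5-10% positive rate and 62-82% detection. The size of the gain is conditional. It is largest at 62% detection, the row that fits the planning rate, and clearly smaller at 80-82%. The smaller-effect figures rest on an assumed share of cases averted, and all figures rest on no effect in screen-negative women.

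The stratum result answers a narrower question, namely the effect among women above the cut-off. It would miss any effect of disclosing a negative result, so it supplements the primary and does not replace it.

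**What to change.** - Keep the all-women intention-to-treat comparison of term preeclampsia as primary and adjust it for screen status (above or below the cut-off).
- Name as a key secondary analysis the between-arm difference in term preeclampsia, with 95% CI, among women above the cut-off in both arms. Test it only after the primary, so that the primary alpha is untouched.
- State that samples are taken and assayed identically in both arms, that concealed-arm ratios stay masked until database lock, and that completeness of the ratio is reported by arm.
- If the analysis plan already contains this, a cross-reference is enough.

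Cost: a few sentences and no extra participants, provided that concealed-arm samples are already being assayed. If they are not, the cost is those assays, and the sponsor should confirm this first.

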**Outcome variables**

Main outcome variables: development of term preeclampsia.

Secondary outcome variables:

- Caesarean section rate
- Incidence of perinatal complications defined as the presence of placental abruption, severe fetal growth restriction (defined as birth weight <3rd centile), perinatal mortality, an Apgar score at 5-minute below 7.0, an umbilical artery pH below 7.10, need for respiratory support within 72 hours after birth neonatal intraventricular haemorrhage grade III/IV, necrotizing enterocolitis, periventricular leukomalacia, sepsis, bronchopulmonary dysplasia or hypoxic ischemic encephalopathy.
- Incidence of maternal complications, defined by a composite including any of the following: (i) HELLP syndrome (lactate dehydrogenase [LDH] >700 IU/L, AST to twice normal values and platelet count <100x10^9/L); (ii) Central nervous system dysfunction (eclampsia, Glasgow Coma Score <13 (12), stroke, reversible ischemic neurological deficit or cortical blindness); (iii) hepatic dysfunction (INR >1.2 in the absence of disseminated intravascular coagulation, MELD score >10 (16), or hepatic hematoma or rupture); (iv) renal dysfunction (dialysis, serum creatinine concentration greater than 150 µmol/L, or urine output <0.5 mL/kg/h during 12 hours, according to renal insufficiency by RIFLE criteria; or need for treatment with furosemide to maintain urine output >0.5 mL/kg/h for 3 hours); (v) respiratory dysfunction (pulmonary edema, requirement of invasive or non-invasive mechanical ventilation, oxygen requirement greater than 50% concentration for longer than 1 hour, or severe breathing difficulty [no criteria of pulmonary edema but presence of dyspnea, crackles in pulmonary auscultation, and SaO2<90%]); (vi) cardiovascular dysfunction (need for inotropic support, left ventricle failure, or myocardial infarction); (vii) placental abruption; or, (viii) a requirement for transfusion of blood products.
- Maternal blood pressure and endothelial function 6-months postpartum.
- Maternal and neonatal hospital stay duration (days).
- Maternal satisfaction and experience assessed by questionnaires (PSS, STAI, WHO and Labor Agency scale).

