### **Randomization**

This will be an open-label randomized trial with parallel groups. An online service (<http://www.clinapsis.com>) will be used to generate a randomised sequence for the block of 1000 participants.

The allocation will be sequestered internally by a Clinical Trials Unit. After enrolment, recruiting physicians will obtain the allocation group from the Unit. Due to the nature of the interventionism it is not possible to blind participants or physicians from the Obstetric Department; however, obstetric management will follow similar protocols in each of the participating centers.

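### The primary outcome, term preeclampsia, has no operational definition, so nothing keeps the ratio revealed in one arm out of the endpoint

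*Protocol*

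**What the plan says.** Under Outcome variables, the primary endpoint is a single line: "Main outcome variables: development of term preeclampsia". No blood pressure threshold, proteinuria or organ-dysfunction criterion, named standard or time window follows. The same section does give laboratory cut-offs for a component of a secondary outcome: "HELLP syndrome (lactate dehydrogenase [LDH] >700 IU/L, AST to twice normal values".

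The only definition of preeclampsia is in the Background, where the condition is "defined as the presence of hypertension with other signs of endothelial systemic damage". The other signs are not listed there.

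Three further statements bear on how a case might be classified:

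- The Background section on angiogenic factors says of sFlt1/PlGF: "This ratio has now been accepted as a criterion for the diagnosis of PE in suspected cases".
- The synopsis, under Intervention, says of the revealed arm: "The result will be known by managing clinicians". In the concealed arm the result is unknown and follow-up is routine.
- The Randomization section says that "it is not possible to blind participants or physicians from the Obstetric Department". Data collection and analysis has research staff abstract outcome data from medical records.

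Within the trial, the ratio is used for screening. The Executive summary describes "screening of term PE with sFlt-1/PlGF ratio in asymptomatic nulliparous women", and the section on the 90th centile sets the cut-offs: "25 between 35+0 and 35+6; and 35 between 36+0 and 36+6".

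**The concern.** The arms differ by design in whether clinicians know the ratio. If knowledge of the ratio can also decide whether a woman is counted as a case, the intervention enters its own endpoint. Take two women with the same clinical picture: new hypertension, no other recorded sign and a high ratio at screening. In the revealed arm the chart may label this preeclampsia on the strength of the ratio. In the concealed arm the trial result cannot be used in that way. The protocol neither permits nor excludes this.

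Through this route extra cases arise in the revealed arm, so a true reduction would be understated or missed. A larger sample would not remove the bias. Nor can the later analysis repair it if the component values behind each diagnosis were never recorded. For that reason the definition belongs in the protocol and is not a detail to leave to an analysis plan.

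**Working it through.** **1. What the text settles about the endpoint**

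- The Background phrase makes hypertension necessary, so a high ratio alone is not preeclampsia.
- It does not say which other signs suffice, or whether an abnormal ratio is one of them.
- The section on angiogenic factors gives the ratio a diagnostic role in suspected cases in general. No section gives the trial's screening value such a role, and none excludes it.
- The statement under Randomization that management follows similar protocols concerns obstetric care across centres, not classification of the endpoint.
- No section shown describes adjudication or masked classification. The Statistical analysis text breaks off in mid-sentence, but nothing shown points to a definition elsewhere.

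**2. The plan's sample size, reproduced**

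Inputs (Sample size calculation): 1.5% concealed, 0.75% revealed, alpha 0.05, power 0.90, ratio 1:1. A two-sided test with unpooled variance gives

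n per arm = (1.960 + 1.2816)² × (0.0075 × 0.9925 + 0.015 × 0.985) / 0.0075² = 4150.4, rounded up to 4151.

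The total is 2 × 4151 = 8302, which is the stated figure.

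Expected events per arm of 4151:

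- Revealed: 0.0075 × 4151 = 31.1
- Concealed: 0.015 × 4151 = 62.3

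**3. Sensitivity to extra revealed-arm cases**

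Let x be the number of women in the revealed arm counted as cases only because the ratio was known. Assume no extra cases in the concealed arm. Then q = 0.0075 + x/4151, d = 0.015 − q, SE = √{[q(1 − q) + 0.015 × 0.985]/4151}, and power is approximately Φ(d/SE − 1.960).

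| x | Revealed events | d | SE | d/SE | Power | Apparent reduction |
|---|---|---|---|---|---|---|
| 0 | 31.1 | 0.00750 | 0.00231 | 3.24 | 90% | 50% |
| 4 | 35.1 | 0.00654 | 0.00236 | 2.77 | 79% | 1 − 35.1/62.3 = 44% |
| 11 | 42.1 | 0.00485 | 0.00245 | 1.98 | 51% | 1 − 42.1/62.3 = 32% |

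The pooled-variance formula gives the same rounded powers. The values of x are chosen to show sensitivity; the documents give no labelling rate.

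**4. The same with an offset in the concealed arm**

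If ratios ordered clinically in the concealed arm also produced 4 extra cases, events would be 35.1 against 66.3. Then d = 0.00750, SE = 0.00241, d/SE = 3.11 and power is 88%. What matters is the net difference between arms.

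**The case against.** The strongest objection is that the mechanism is inferred from silence. The trial ratio is a screening value in asymptomatic women, with cut-offs derived from uneventful pregnancies. Its diagnostic role is mentioned once, in background text, and only for suspected cases. Nothing shows that abstractors would count a result from 35 to 36 weeks as the second sign. This stands as a limit on the claim: exposure is documented, occurrence is not. It does not supply the missing definition.

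The asymmetry is also incomplete. A hypertensive woman in the concealed arm is a suspected case, and the protocol does not bar a separately ordered ratio. This stands too. The 79% and 51% figures assume no such offset; step 4 shows 88% when 4 extra cases arise in each arm.

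A reader might infer that the trial is biased towards no effect overall. The documents do not support that. Counting the ratio as a criterion would add revealed-arm cases, but a reassuring low ratio could reduce work-up in that arm and act the other way. The net direction of all ascertainment differences cannot be fixed from the text.

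It is also tempting to express 4 or 11 cases as a share of all women with a high ratio, which would make the threshold look easy to reach. That is the wrong denominator. Only flagged women who become hypertensive without another sign could be labelled in this way, and the documents give no rate for them.

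**Conclusion.** The point holds as a gap in the definition of the primary endpoint. The protocol names term preeclampsia without criteria that an abstractor could apply, and nothing stops the ratio, revealed in one arm only, from contributing to the diagnosis. The sample size arithmetic is unaffected.

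The consequence is conditional. If the revealed ratio were counted as the second sign in hypertensive women, the treatment effect would be diluted. With about 31 against 62 expected events, small net counts matter: 4 extra revealed-arm cases cost about 11 percentage points of power, and 11 leave it near one half. These figures rest on the protocol's own rates, 4151 women per arm, a two-sided 5% test and no extra concealed-arm cases. They are not estimates of what will happen.

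The documents do not show that such labelling will occur, how often it would, or that the net bias runs one way. The change should be made, with medium confidence in its practical importance.

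**What to change.** Under Outcome variables:

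1. State one research definition of term preeclampsia, taken from a recognised standard of the sponsor's choice and applied identically in both arms to recorded component values.
2. State that the trial sFlt1/PlGF ratio is not an endpoint criterion, and set one rule for both arms on ratios ordered separately in clinical care.
3. Have the existing abstraction staff record the component values on the case report form, so that cases can be classified without sight of the ratio or the allocation where feasible.

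The cost is outcome wording, a case-report-form rule and some extra abstraction; the sample size and the intervention do not change. Some cases labelled by clinicians will not count. Masking will be incomplete, because charts may show the ratio or the reason for induction. The change does not correct under-diagnosis through reassurance, or differences between arms in how often blood pressure is measured or tests are done.
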